5.2.1. Legislation and guidelines used for preparation

867 The present clinical trial will be conducted in accordance with the published principles of the
868 guidelines for Good Clinical Practice (ICH-GCP). These principles cover, amongst other
869 aspects, ethics committee procedures, the obtaining of informed consent from trial subjects,
870 adherence to the trial protocol, administrative documentation, data collection, trial subjects'
871 medical records (source documents), documentation and reporting of adverse events (AEs),
872 preparation for inspections and audits, and the archiving of trial documentation. All
873 investigators and other staff directly concerned with the study will be informed that domestic
874 and foreign supervisory bodies, the competent federal authorities and authorised
875 representatives of the responsible institution have the right to review trial documentation and
876 the trial subjects' medical records at any time.

877

5.3. Registration

878 Before the trial is started, it will be registered under Current Controlled Trials
879 (www.controlled-trials.com) or another trial register approved by the World Health
880 Organisation (WHO) (<http://www.who.int/ictcp/en/>).

881

5.4. Insurance of trial subjects

882 All trial subjects enrolled are insured under the group insurance contract of University
883 Hospital Münster with HDI Gerling (insurance company). The headquarters, policy number
884 and telephone and fax number will be included in the patient information sheet.

885

5.5. Data protection

886 The provisions of data protection legislation will be observed. It is assured by the responsible
887 institution that all investigational materials and data will be pseudonymised in accordance
888 with data protection legislation before scientific processing.

889 Trial subjects will be informed that their pseudonymised data will be passed on in
890 accordance with provisions for documentation and notification pursuant to § 12 and § 13 of
891 the GCP Regulations to the recipients described there. Subjects who do not agree that the
892 information may be passed on in this way will not be enrolled into the trial.

893 **6. Statistical methods and sample size calculation**

894 **6.1. Statistical and analytical plan**

895 Statistical analyses will be performed according to the principles of the ICH-guideline E9
896 “Statistical Principles for Clinical Trials” using standard statistical software (SAS or SPSS).

897 A group sequential plan according to O’Brian and Fleming with one interim analysis will be
898 applied. In order to maintain a global significance level $\alpha=0.05$, the interim and the final
899 analysis are performed on local significance levels 0.0052 and 0.0480, respectively. Based
900 on the group sequential plan, in the interim analysis the sample size of the final analysis will
901 be re-calculated applying the Inverse Normal method⁵³.

902 In the event of important new discoveries the design of the study may be changed. If an
903 adaptation of the design is necessary, the respective changes may be done according to the
904 conditional rejection error probability method^{54,55}.

905 The randomized groups will be descriptively compared on all baseline variables using
906 summary statistics such as mean and standard deviation, median and quartiles, or frequency
907 and percent, as appropriate. The primary efficacy analysis will include all randomized
908 patients (full analysis set) and will be performed according to the intention-to-treat principle,
909 i.e. all patients are analyzed in the group to which they were randomized. Primary efficacy
910 analysis provides confirmatory statistical evidence.

911 Beyond the primary intention-to-treat analysis of the primary outcome, sensitivity analyses
912 will be performed. In per-protocol analyses only patients without major protocol violations are
913 included. I.e. in particular, the included patients have complete 90-day follow-up (complete
914 case analysis). Treatment groups are compared using a two-sided Cochran-Mantel-Haenszel
915 test.

916 **6.1.1. Trial populations**

917 All analyses will be conducted on two trial populations:

918 The primary dataset for analysis is derived from the intention-to-treat (ITT) population. This
919 dataset includes all trial subjects enrolled into the trial and randomized.

920 The secondary dataset for analysis is derived from the per-protocol (PP) population. This
921 dataset includes all trial subjects who were treated according to protocol and reached a
922 defined endpoint in the trial.

923

6.1.2. Primary target variable

924 The effect of early initiation of RRT versus late initiation of RRT on overall survival in a 90-
925 day follow-up period will be assessed by comparing the randomized groups with a (two-
926 sided) Log-rank test.

927 The null hypothesis $H_0: S_0(t)=S_1(t)$ for all t is tested against the (two-sided) alternative H_1 :
928 $S_0(t')\neq S_1(t')$ for any t' , where $S_0(t)$ and $S_1(t)$ denote the overall survival function in the control
929 group and the experimental treatment group, respectively. If the difference in overall survival
930 is significant, the treatment effect will be estimated by means of the 90-day all cause
931 mortality rate in both treatment groups.

932 Further sensitivity analyses of the primary outcome are performed in order to address the
933 following issue. Study patients have a different baseline risk profile. This becomes apparent
934 especially in the control group with late initiation of RRT, where three risk groups may be
935 differentiated. There are “high risk” patients who die before the indication for RRT is reached
936 and “low risk” patients who survive the entire 90-day follow-up period and never show the
937 indication for RRT. The remaining “medium risk” patients (as expected about 80% of control
938 patients) show the indication for RRT at a certain time point in the 90-day follow-up period
939 and RRT is initiated. The efficacy of the experimental and the control treatment may differ
940 depending on the patients’ risk profile. Maybe “high risk” patients benefit from experimental
941 treatment with early initiation of RRT substantially compared to control treatment, whereas in
942 “low risk” patients both treatments are equally efficacious. Moreover it is of interest, if both
943 treatments differ in particular in the “medium risk” subgroup, i.e. in those control patients,
944 who actually received RRT, compared to the corresponding patients in the experimental
945 treatment group. In order to address these questions, multivariable statistical analyses are
946 performed using Cox regression. Overall survival is modelled as a function of baseline risk,
947 RRT treatment, and the interaction of baseline risk and RRT treatment. In three different
948 model approaches, RRT treatment is expressed in terms of (i) a time-dependent covariate
949 that impacts survival starting with the time of RRT initiation, (ii) the randomized treatment
950 group, and (iii) the time to initiation of RRT.

951

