 386 patients receiving care in the critical care units on a daily basis. After obtaining informed
 387 consent and check the randomization criteria, the patient will be registered and
 388 randomization will be carried out by the Institute of Biostatistics and Clinical Research
 389 Münster. Before initiating RRT, laboratory test will be performed and different variables will
 390 be documented including demographic data, APACHE II score, SOFA organ-system score,
 391 etc. In the 'early' group, RRT will be initiated immediately after randomization, whereas
 392 initiation of RRT in the 'late' group will be started after reaching stage 3 of the KDIGO
 393 classification and/or if absolute indications for RRT will be present. Laboratory tests will be
 394 analyzed and variables relevant for the assessment of illness severity will be recorded.

395 SOFA Organ Failure Score at different days, length of ICU stay, length of hospitalization, 28-
396 day all cause mortality, recovery of renal function and requirement for hemodialysis after day
397 28 and day 60, duration of renal replacement therapy, 60-day all cause mortality, 90-day all
398 cause mortality, cost analysis of renal replacement therapy, and 1 year mortality will be
399 documented at follow-up visits up to one year. * Absolute indications for the initiation of RRT
400 are 1) urea serum levels > 100mg/dl, 2) potassium serum levels > 6mmol/l and/or ECG
401 abnormalities, 3) magnesium serum levels > 4mmol/l and/or anuria/absence of deep tendon
402 reflexes, 4) blood pH < 7.15, 5) urine production < 200ml/12h or anuria, and 6) organ edema
403 in the presence of AKI resistant to diuretic treatment ⁴⁴.

404 **4.2. Discussion of trial design**

405 Renal replacement therapy is the main treatment option for AKI. To investigate the
406 appropriate time point of initiation of RRT, we will randomly assign patients to receive early
407 (KDIGO stage 2) or late (KDIGO stage 3 or if absolute indications for RRT are present)
408 initiation of RRT. A placebo group of patients with acute kidney injury withheld from RRT is
409 ethically not acceptable. The currently accepted, absolute indications for the initiation of RRT
410 are

- 411 1) urea serum levels > 100mg/dL,
- 412 2) potassium serum levels > 6mmol/L and/or ECG abnormalities,
- 413 3) magnesium serum levels > 4mmol/L and/or anuria/absence of deep tendon
414 reflexes,
- 415 4) blood pH < 7.15,
- 416 5) urine production < 200mL/12h or anuria, and

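### Section 6.1.2 asks for a medium-risk comparison whose groups are defined by events after randomisation in controls; early-arm members cannot be identified, and the planned Cox models do not estimate it

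*Protocol*

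**What the plan says.** Section 6.1.2 plans further sensitivity analyses of the primary outcome because patients differ in baseline risk. It says that this shows "especially in the control group with late initiation of RRT, where three risk groups may be" distinguished. The groups are:

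- **High risk:** "patients who die before the indication for RRT is reached".
- **Low risk:** those who live through all 90 days and never reach the indication.
- **Medium risk:** the rest, expected to be about 80% of controls, who reach the indication and start RRT.

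The section then asks whether the treatments differ in the medium-risk subgroup, that is, in the controls "who actually received RRT, compared to the corresponding patients in the experimental" group. To answer these questions it plans Cox models of survival on baseline risk, "RRT treatment, and the interaction of baseline risk and RRT treatment". RRT is coded in three ways: (i) as a time-dependent covariate, (ii) as the randomised group and (iii) as time to initiation. The section names no variable or score as baseline risk.

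For the early arm, the text accompanying Figure 1 (section 4.1.1) says: "RRT will be initiated immediately after randomization, whereas" the late arm waits for KDIGO stage 3 or an absolute indication.

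**The concern.** The groups are called baseline risk, but none of them is known at baseline. Each describes how a patient fares under late initiation. In the early arm that course is never seen, because RRT starts before it can unfold. The corresponding early-arm patients exist in principle but cannot be picked out of the data, and the protocol gives no rule or assumption for finding them.

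In controls, two of the groups also encode the outcome: everyone in the high-risk group dies and nobody in the low-risk group does. Restricting the control arm to RRT recipients therefore removes a selected set of deaths and a selected set of survivors from one arm only. A result obtained this way, reported as a sensitivity analysis of the primary outcome, could be read as supporting or undermining the main finding when it reflects only who was removed.

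**Working it through.** **Inputs from the protocol.** Medium-risk share of controls about 80% (6.1.2). Expected 90-day mortality 55% late and 37% early, and 106/0.46 = 230 evaluable patients (6.2). Allocation 1:1 (4.1), so 115 per arm; 0.80 × 115 = 92 controls in the medium group and 23 outside it. The 80% is the only figure given for this analysis, so there is no stated result to reproduce.

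**Assumptions.** Let h be the share of controls who die before the indication. The protocol does not give it. High and low risk together make up 20%, and the text says that both groups exist, so h lies strictly between 0% and 20%. I use 5% to 15% as an illustrative range and show the limits. Every control who reaches the indication is taken to start RRT, as the section describes.

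**Step 1: mortality in control RRT recipients.** High-risk patients contribute h deaths and low-risk patients none, so mortality in the medium group is (0.55 - h)/0.80.

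**Step 2: no treatment effect, 55% in both arms.** The simplest comparator is the whole early arm. The false early-minus-late difference is 0.55 - (0.55 - h)/0.80. The last column is the approximate rejection rate of a nominal two-sided 5% comparison of proportions, 92 against 115 patients.

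| h | Control RRT recipients | False difference (points) | Rejection rate |
|---|---|---|---|
| 0% (limit) | 68.8% | -13.8 | 54% |
| 5% | 62.5% | -7.5 | 19% |
| 10% | 56.3% | -1.3 | 5% |
| 15% | 50.0% | +5.0 | 11% |
| 20% (limit) | 43.8% | +11.3 | 37% |

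The difference is zero when (0.55 - h)/0.80 = 0.55, that is, h = 0.55 - 0.44 = 0.11.

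**Step 3: what the data can say without assumptions, at the planned effect.** By randomisation the early arm also contains about 80% latent medium-risk patients. If the other 20% all die, mortality in the medium group is (0.37 - 0.20)/0.80 = 21.3%. If none of them die, it is 0.37/0.80 = 46.3%. With h = 10% the medium-risk effect lies anywhere from 21.3 - 56.3 = -35 to 46.3 - 56.3 = -10 points. This 25-point width is not sampling error and would not shrink with more patients.

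**Step 4: do the Cox models answer the question?** There are two readings of baseline risk.

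- If it means the three groups, it has no value in the early arm and contains the outcome in the control arm.
- If it means a score from values before randomisation, model (ii) is a sound analysis of effect by risk, but its interaction is not the effect in patients who would have received RRT under late initiation.

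Neither reading gives the stated contrast. A simulation with no treatment effect points the same way. It used about 20,000 patients per arm and an assumed frailty driving both death and the indication; about 10% of controls were high risk and 83% to 87% medium. The early-versus-late hazard ratio among RRT-treated patients was 1.02 to 1.14. Model (ii) with a true baseline covariate gave 0.98 to 1.00, with interaction 0.98 to 1.02.

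**The case against.** The best defence is that the three groups only motivate the analysis. The section speaks of a baseline profile that becomes apparent in controls, and the analysis itself is the Cox regression. Nothing says that the groups enter as covariates or subgroups, and the choice of baseline variables can properly be left to a statistical analysis plan. This stands in part: a reader might infer that the outcome-defined groups will be put into the model, and the text does not say so. It does not rescue the medium-risk question. The protocol itself sets that contrast and says that these models address it, and no choice of baseline covariates makes them do so.

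Other objections limit the size. The whole early arm is not the only possible comparator; a weighted or modelled one could be built, but it needs assumptions that the protocol does not state. The limits h = 0% and h = 20% each empty a group that the protocol says exists. Near h = 11% the bias cancels.

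A reader might also infer that the high-risk comparison must favour early RRT. That does not follow: no early-arm patient can be classified, so no such comparison exists in the data. Nor can the contrast in step 2 manufacture or erase the whole design effect of 55 - 37 = 18 points; its largest error is 13.8 points.

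**Conclusion.** The point holds for the medium-risk contrast. As written it is not identified, and the models named for it do not estimate it. In the illustration the false difference is -7.5 to +5.0 points for h from 5% to 15%, with limits of -13.8 and +11.3. Because the sign depends on a split that the protocol does not give, neither direction nor size can be claimed in advance. The figures rest on the protocol's 80% and 55%, on the whole early arm as comparator and, for the false differences, on no treatment effect.

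A reader might infer that the trial's main conclusion is at risk. The documents do not support that. These are sensitivity analyses, and the synopsis makes only the primary efficacy analysis confirmatory and everything else explorative. The intention-to-treat log-rank test and the sample size do not depend on the risk groups. The change is worth making because the contrast cannot be interpreted as it stands and the correction is cheap.

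**What to change.** In section 6.1.2:

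1. State that baseline risk is built only from values recorded before randomisation, in the same way in both arms. Candidates are the two stratification factors in section 4.2.1 (cardiovascular SOFA 0-2 or 3-4, and oliguria), age and screening SOFA. APACHE II is also possible, but Table 3 lists it at baseline and not at screening, so its component values must predate randomisation.
2. State that none of the three described groups is used as a covariate or subgroup.
3. Take the interaction of risk with randomised group (model ii), in all randomised patients, as the analysis of effect by risk.
4. Drop the medium-risk contrast, or restate it as an exploratory principal-stratum estimand with its untestable assumptions and bounds such as those in step 3. Only about 23 of 115 controls would fall outside the stratum, so any model predicting membership will be imprecise.

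The cost is a change of wording and some analysis work, with no new data. The drawback is that a baseline score separates patients less sharply than groups defined by outcome, and the interaction estimate will be imprecise.

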981 Power calculations are performed based on the primary endpoint, i.e. the overall survival in a
982 90-day follow-up period (90-day all cause mortality). The primary efficacy analysis is
983 intended to show superiority of early versus late initiation of RRT in intensive care patients
984 with acute kidney injury. An upper bound of the required number of patients is determined,
985 assuming that in the worst expected case 10% of recruited patients have completely non-
986 evaluable data.

987 A group sequential plan according to O'Brien and Fleming with one interim analysis and a
988 global (two-sided) significance level $\alpha=0.05$ is applied. The expected 90-day mortality
989 rate in the control group with late initiation of RRT is 55%. Differences between treatment
990 groups are to be detected with a power of 80%, if the 90-day mortality rate in the
991 experimental intervention group with early initiation of RRT is 37% or smaller. The expected
992 treatment effect is substantiated by published data and clinical reasoning. The interim
993 analysis is conducted using half of the total number of patients (information rate 0.5).
994 Resulting from these considerations, interim analysis is performed after 53 deaths have been
995 observed across both treatment groups. The final analysis is performed after 106 deaths
996 have been observed across both treatment groups. I.e. assuming an average 46% mortality
997 rate in the 90-day follow-up period, a total number of $106/0.46=230$ patients across both
998 treatment groups is included in the final analysis. This corresponds to 250 recruited
999 patients. Power calculations were performed using the ADDPLAN software.

1000 **Compliance / Rate of loss to follow up**

1001 Approximately 5-10% of recruited patients are expected to be lost to follow-up during the 90-
1002 day follow-up period. In terms of a worst-case approach in the power analysis, dropout
1003 patients are assumed to have completely non-evaluable data. Therefore in order to ensure
1004 that 240 evaluable patients exist, 260 patients will be recruited. Apart from this worst-case
1005 approach pursued in power calculations, in the primary analysis dropout patients in fact are
1006 included.

1007 **7. Safety**

1008 **7.1. Definitions of adverse events**

1009 **7.1.1. Adverse event**

1010 An adverse event (AE) is any untoward medical occurrence in a trial subject administered an
1011 IMP. There does not necessarily have to be a causal relationship with this treatment.

1012 Concomitant diseases

1013 The deterioration of a preexisting illness is also an AE in the context of a clinical trial. The
1014 following, however, is not regarded as an AE: a preexisting disease that led to a planned
1015 treatment measure before the start of the clinical trial, e.g. admission to hospital as an
1016 inpatient. This should be made clear in the trial subject's medical records and should also be
1017 documented in the CRF (see Section 7.1.2).

1018 **7.1.2. Serious adverse events**

1019 A serious AE (SAE) is any untoward medical occurrence that at any dose

- 1020 1. Results in death,
- 1021 2. Is life-threatening at the time of the event
- 1022 3. Requires inpatient hospitalisation or prolongation of existing hospitalisation
- 1023 4. results in persistent or significant disability/incapacity
- 1024 5. is a congenital anomaly or birth defect (1.-4.: § 3(8) GCP Regulations)
- 1025 6. In the opinion of the investigator, fulfils any other criteria similar to 1.-4.

1026 Inpatient hospitalisation is defined as any stay in hospital on the part of a trial subject that
1027 includes at least one night (midnight to 06:00). Admission to hospital as an inpatient planned
1028 before the first admission of the IMP are not SAEs, but must be documented in the proper
1029 manner in the trial subject's medical records and CRF (see Section 7.1.1).

1030 **7.2. Documentation and follow-up of adverse events**

1031 The responsible institution ensures that all persons involved in the treatment of trial subjects
1032 are adequately informed of the responsibilities and actions required when AEs occur. Trial

1033 subjects will be asked at each visit whether they have experienced AEs or SAEs. AEs will be
1034 documented in the trial subject's medical records.

1035 **7.2.1. Documentation of complications**

1036 All complications due to RRT will be documented in the CRF.

1037

1038 **8. Use of trial findings and publication**

1039 **8.1. Reports**

1040 **8.1.1. Final report**

1041 The ethics committee will be informed within 90 days that the trial has officially ended.

1042 Within one year of the completion of the trial, the ethics committee will be supplied with a
1043 summary of the final report on the clinical trial containing the principle results.

1044 **8.2. Publication**

1045 It is planned to publish the trial results, in mutual agreement with the PCI, in a scientific
1046 journal and at German or international congresses. Publication of the results of the trial as a
1047 whole is intended. Any publication will take account of the '(International Committee of
1048 Medical Journal Editors' (ICMJE))⁵⁶.

1049 The trial will also be registered in a public register in accordance with the recommendations
1050 of the ICMJE (see also Section 5.3).

1051 Any published data will observe data protection legislation covering the trial subject and
1052 investigators.

1053

1054 **9. Amendments to the trial protocol**

1055 To ensure that comparable conditions are achieved in the interests of a consistent and valid
1056 data analysis, changes to the provisions of this trial protocol are not planned. In exceptional
1057 cases, however, changes may be made to the trial protocol. Such changes can only be made
1058 if agreed by the institution, the PCI and biometrician, and all Authors of this trial protocol.
1059 Any changes to the trial procedures must be made in writing and must be documented with
1060 reasons and signed by all Authors of the original trial protocol.

1061 Amendments made in accordance with § 10 Secs. 1 and 4 GCP Regulations that require
1062 approval are submitted to the ethics committee and the supreme federal authority and will
1063 not be implemented until approved. Exceptions to this are amendments made to avoid
1064 immediate dangers.

1065 **10. References**

- 1066 1. Brivet FG, Kleinknecht DJ, Loirat P, Landais PJ. Acute renal failure in intensive care
1067 units--causes, outcome, and prognostic factors of hospital mortality; a prospective,
1068 multicenter study. French Study Group on Acute Renal Failure. *Crit Care Med*
1069 1996;24:192-8.
- 1070 2. Uchino S, Kellum JA, Bellomo R, et al. Acute renal failure in critically ill patients: a
1071 multinational, multicenter study. *Jama* 2005;294:813-8.
- 1072 3. Bellomo R, Ronco C, Kellum JA, Mehta RL, Palevsky P. Acute renal failure -
1073 definition, outcome measures, animal models, fluid therapy and information
1074 technology needs: the Second International Consensus Conference of the Acute
1075 Dialysis Quality Initiative (ADQI) Group. *Crit Care* 2004;8:R204-12.
- 1076 4. Bagshaw SM, George C, Dinu I, Bellomo R. A multi-centre evaluation of the RIFLE
1077 criteria for early acute kidney injury in critically ill patients. *Nephrol Dial Transplant*
